Because the AATD requires sets of equal difficulty, the word sets are made of novel words balanced for number of phonemes and syllables, phonotactic probability, and lexical neighborhood density (Storkel, 2003; Storkel & Hoover, 2010a, 2010b). Novel words nearly eliminate the possibility of prior exposure and enable the creation of balanced word sets. Early developing consonants and tense vowels expected to be in the participants' phonemic repertoires (assessed prior to baseline) are primarily used, which aids acquisition receptively and expressively (Leonard et al., 1982). Words do not contain high frequency phonemes (based on acoustic frequency) because they influence word learning and are more likely to be less audible, inaudible, or distorted than lower frequency phonemes for DHH children (Niskar et al., 1998; Shargorodsky et al., 2010; Stelmachowicz et al., 2004b). The following words sets are used: (1) /zod/, /wam/, /getʃ/, and /pib/; (2) /pem/, /vad/, /jotʃ/, and /kub/; (3) /jum/, /tetʃ/, /vob/, and /ked/.

Unfamiliar Objects

Each novel word is randomly paired to an unfamiliar object (e.g., building sets and hardware store items). Testing prior to baseline ensures that participants do not have a consistent form associated with any unfamiliar object or a meaning associated with any of the novel words.

Semantic Content

During intervention the examiner labels the novel object's location (e.g., toy box or bathtub) to increase semantic content. Including this content provides an early step towards using retrieval practice to teach rich vocabulary content that is necessary for achieving age expected language skills without threatening the study's internal validity. Locations are randomly assigned to avoid objects' perceptual features being associated with locations and pretested to ensure participants have the conceptual knowledge of each location to maintain balanced word sets across conditions.

Procedures

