All sessions are in-person and videorecorded. Participants must pass a listening check to proceed with the session. Sessions take place in a quiet room (ambient noise ≤ 40 dB as measured by a sound level mobile application) in the child's home, educational setting, or clinic, depending on caregiver preference. Flexibility in location to match caregiver preferences is one way we guard against attrition. Having the examiner for all assessments and intervention sessions be a research team member, rather than school personnel, and conducting the intervention for a relatively short period of time are also designed to guard against attrition.

Dependent Variable Probe

The dependent variable probes (about 10 minutes) test the 12 target words in sets by condition. The primary dependent variable is the percent accuracy (i.e., correct responses / total trials x 100) for labeling target words expressively. The examiner asks the child to label the taught unfamiliar objects and one known object per set (i.e., "What's this?"). The participant is given up to 10 seconds to respond. The secondary dependent variables are the percent accuracy for (a) receptively identifying target words within 5 seconds in a field of six (i.e., four target objects, one foil, and a known object), (b) associated semantic information (i.e., location; "Where's this from?"), and (c) phonological precision for labeling target words expressively. The examiner will not provide any feedback regarding response accuracy for target words during the dependent variable probes. To maintain engagement, the examiner may provide positive reinforcement for non-target behaviors and for identifying the known word for each group, which is expected to be particularly important in the early sessions when accuracy for target words is expected to be low. The study's procedural manual specifies how the examiner should respond to specific child behaviors (e.g., self-corrections and articulatory errors). Primary and secondary coders double enter data into an electronic form using direct systematic observation of the video recordings (Ledford & Gast, 2018).

A research assistant codes at least 25% of sessions in each condition for each participant for interobserver agreement (IOA). The primary coder is blind to which sessions are coded for reliability. All coders are trained to .85 point-by-point agreement for independent coding of three consecutive sessions via recordings of non-participants

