4. Examiner asks the participant to label the novel object four times and the location twice for retrieval practice

Feedback condition: Examiner provides direct feedback on accuracy and labels the target word (e.g., "Yes, that is a X!" or "Oops, that is a X!")

No-feedback condition: Examiner says statement without target word and then one with it to provide equal exposures to the feedback conditions (e.g., This looks neat. Here's the X!)

5. After the first word, examiner completes same procedure with the three remaining target words in the set
6. Examiner concludes set by asking participant to label and identify the picture for each word and state its location

Feedback condition: Examiner provides direct feedback without naming the target word

No-feedback condition: Examiner does not provide feedback and proceeds to next item

After a participant reaches the criterion of 75% accuracy for expressive labeling for three consecutive sessions for the four target words for one condition, instruction in the remainder of the comparison phase is provided only in the unmastered condition. The comparison phase ends when the unmastered condition reaches criterion. If the participant does not reach mastery after two times the number of sessions to criterion in the mastered condition, the maintenance phase begins then.

Maintenance Phase

Maintenance data are collected weekly via baseline procedures. Maintenance data are first collected a week after the participant achieves mastery for at least one condition. The same dependent variable probe used for the baseline and comparison phases is used to collect maintenance data. Sessions continue for 4 weeks after the comparison phase to permit sufficient time for a trend to emerge for visual analysis. If a consistent pattern is observed before 4 weeks have elapsed, the maintenance phase will end at that time. For example, the maintenance phase ends if a participant exhibits 0% accuracy for all conditions for two consecutive sessions.

Procedural Fidelity

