8.0 Statistical Considerations

Visual Analysis

Visual analysis is the primary analysis method for single case research design (Ledford & Gast, 2018). Consistent with What Works Clearinghouse practices, we consider five features of the data pattern: level, trend, variability, overlap, and consistency (Kratochwill et al., 2010). We use visual analysis to determine whether there is functional relation between the independent variable (i.e., specific retrieval practice component) and the dependent variable. For each participant with the relevant conditions in their contrast, we examine whether there is evidence of a functional relation between the independent variable and dependent variable. We combine across participants based on the What Works Clearinghouse criteria for strong, moderate, and no evidence of an effect (What Works Clearinghouse, 2016).

Research questions related to effectiveness of the active interventions (i.e., RQs 1-4 and 7-10) will be judged based on accuracy for words taught in the active intervention condition versus those in the no-teaching condition. Research questions related to efficiency (i.e., RQs 5, 6, 11, and 12) will be judged based on accuracy for words taught in one active condition versus those taught in the other (e.g., retrieval practice with versus without feedback).

Feedback. Participants ($n = 8$) in Contrasts A (feedback vs. no feedback with massed trials) and B (feedback vs. no feedback with spaced trials) address the effect of feedback (see Figure 1). Table 2 displays how we will compare conditions within Contrasts A and B to evaluate both effectiveness and efficiency research questions. For all of these analyses, we use expressive labeling as the primary dependent variable. Therefore, performance for expressive labeling determines when phases change. Phonological precision, receptive performance, and knowledge of semantic content (i.e., location) are secondary variables that will be considered when interpreting the overall results. For example, one condition may exhibit greater accuracy for the primary dependent variable, but not for one or more of the secondary variables.

Figure 1
Study Contrasts

	Feedback	No feedback	Contrasts to Determine Effect of Feedback (RQs 1-6)
Massed	Feedback with massed trials	No feedback with massed trials	Contrast A: Feedback vs. no feedback (massed trials)
Spaced	Feedback with spaced trials	No feedback with spaced trials	Contrast B: Feedback vs. no feedback (spaced trials)

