Contrasts to Determine Effect of Spacing (RQs 7-12)	Contrast D: Spaced vs. massed trials (with feedback)	Contrast C: Spaced vs. massed trials (no feedback)	

Table 2. *Comparisons of Relevant Conditions for the Effect of Feedback*

Research question		Contrast	Condition 1	Condition 2	Phase	Feedback RQs
Effectiveness or efficiency	Acquisition or retention					
Effectiveness	Acquisition	A	Feedback w/massed trials	No-teaching control	Comparison	1
		B	Feedback w/spaced trials	No-teaching control	Comparison	1
		A	No feedback w/massed trials	No-teaching control	Comparison	2
		B	No feedback w/spaced trials	No-teaching control	Comparison	2
Effectiveness	Retention	A	Feedback w/massed trials	No-teaching control	Maintenance	3
		B	Feedback w/spaced trials	No-teaching control	Maintenance	3
		A	No feedback w/massed trials	No-teaching control	Maintenance	4
		B	No feedback w/spaced trials	No-teaching control	Maintenance	4
Efficiency	Acquisition	A	Feedback w/massed trials	No feedback w/massed trials	Comparison	5
		B	Feedback w/spaced trials	No feedback w/spaced trials	Comparison	5
Efficiency	Retention	A	Feedback w/massed trials	No feedback w/massed trials	Maintenance	6
		B	Feedback w/spaced trials	No feedback w/spaced trials	Maintenance	6

Effectiveness. For research questions related to effectiveness, we determine whether there is an increase in accuracy for the active retrieval practice condition without an

accompanying increase, or with a smaller increase, for the no-teaching control condition. Given that the target words are novel words, participants are not expected to show increased accuracy for the dependent variables for the control condition.

For effectiveness of retrieval practice with feedback for *acquisition* (RQ1), we determine whether there is a separation of the data paths (as indicated by visual analysis and statistical analyses) for (a) the retrieval practice with feedback with massed trials condition and the no-teaching control condition and (b) the retrieval practice with feedback with spaced trials condition and the no-teaching control condition in the comparison phase. This separation of the data paths with the retrieval practice condition above the no-teaching condition in the comparison phase would provide evidence of the effectiveness of retrieval practice with feedback.

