		D	Feedback w/spaced trials	No-teaching control	Comparison	7
		C	No feedback w/massed trials	No-teaching control	Comparison	8
		D	Feedback with massed trials	No-teaching control	Comparison	8
Effectiveness	Retention	C	No feedback w/spaced trials	No-teaching control	Maintenance	9
		D	Feedback w/spaced trials	No-teaching control	Maintenance	9
		C	No feedback w/massed trials	No-teaching control	Maintenance	10
		D	Feedback with massed trials	No-teaching control	Maintenance	10
Efficiency	Acquisition	C	No feedback w/massed trials	No feedback w/spaced trials	Comparison	11
		D	Feedback w/massed trials	Feedback w/spaced trials	Comparison	11
Efficiency	Retention	C	No feedback w/massed trials	No feedback w/spaced trials	Maintenance	12
		D	Feedback w/massed trials	Feedback w/spaced trials	Maintenance	12

Effectiveness. For research questions related to effectiveness, we determine whether there is an increase in accuracy for the active retrieval practice condition without an accompanying increase, or with a smaller increase, for the no-teaching control condition. Given that the target words are novel words, participants are not expected to show increased accuracy for the dependent variables for the control condition.

For effectiveness of retrieval practice with spaced trials for *acquisition* (RQ7), we determine whether there is a separation of the data paths for (a) the retrieval practice without feedback with spaced trials condition and the no-teaching control condition and (b) the retrieval practice with feedback with spaced trials condition and the no-teaching control condition in the comparison phase. This separation of the data paths with the retrieval practice condition above the no-teaching condition in the comparison phase would provide evidence of the effectiveness of retrieval practice with spaced trials.

For effectiveness of retrieval practice with massed trials for *acquisition* (RQ8), we determine whether there is a separation of the data paths for (a) the retrieval practice without feedback with massed trials condition and the no-teaching control condition and (b) the retrieval practice with feedback with massed trials condition and the no-teaching control condition in the comparison phase. This separation of the data paths with the retrieval practice condition above the no-teaching condition in the comparison phase would provide evidence of the effectiveness of retrieval practice with massed trials.

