For efficiency of retrieval practice with spaced versus massed trials for *retention* (RQ12), we determine whether there is a separation of the data paths for (a) the retrieval practice without feedback with massed trials condition and the retrieval practice without feedback with spaced trials condition (Contrast C) and (b) the retrieval practice with feedback with massed trials condition and the retrieval practice with feedback with spaced trials condition (Contrast D) in the maintenance phase. The number of sessions to fall below mastery is also considered when determining the presence of a functional relation related to efficiency. This separation of the data paths in the maintenance would provide evidence of greater efficiency for the condition with the path that is displayed higher on the graph.

Statistical Analysis

There is no consensus on recommended statistical analyses for single case research designs, particularly for the adapted alternating treatments design, which is underrepresented in research on the use of statistical analyses and effect sizes in single case research. We will calculate Nonoverlap of All Pairs (NAP; Parker & Vannest, 2009), an overlap-based effect size, and analyze differences in conditions analogous to those described for visual analysis. Because overlap is one feature used for determining a functional relation, NAP will provide guidance on the degree of confidence for inferring the amount of overlap between conditions. NAP is defined as the number of comparison pairs between phases A and B without overlap divided by the total comparisons. It is related to Tau, another overlap metric. Tau is a linear re-scaling of NAP (Zimmerman et al., 2018). NAP offers several advantages over other overlap-based effect sizes, including less human error in calculations (can be calculated by hand or via computerized methods), stronger validation by R^2 , and narrower confidence intervals (Parker & Vannest, 2009). Parker and Vannest (2009) tentatively suggest the following guidelines for NAP effect sizes: .93 – 1.00 = large, .66 – .92 = medium, and 0 – .65 = weak.

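### If the untaught words stay at 0% as expected, NAP for expressive labeling in the eight effectiveness questions shows only whether any word was correct, so its size labels can mislead

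*Combined protocol and SAP*

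**What the plan says.** Section 8.0 judges the effectiveness questions (RQs 1-4 and 7-10) by comparing an active set with the no-teaching set. Effectiveness means a rise in the active set without an "accompanying increase, or with a smaller increase, for the no-teaching control condition". Of the untaught words it says that "participants are not expected to show increased accuracy for the dependent variables for the control condition". The pretest described in section 5.0 (Unfamiliar Objects) supports that expectation: "Testing prior to baseline ensures that participants do not have a consistent form associated with any unfamiliar object".

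On the outcome, section 5.0 states: "The primary dependent variable is the percent accuracy (i.e., correct responses / total trials x 100) for labeling target words expressively". Each set has four words. Mastery is the "criterion of 75% accuracy for expressive labeling for three consecutive sessions for the four target words for one condition".

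On the statistic, section 8.0 (Statistical Analysis) calls NAP an overlap-based effect size and applies it to the same contrasts as the visual analysis. "NAP is defined as the number of comparison pairs between phases A and B without overlap divided by the total comparisons". Scoring of ties is not stated. The bands, credited to the method's authors as tentative, are "93 – 1.00 = large, .66 – .92 = medium, and 0 – .65 = weak", where the first figure is .93. Visual analysis, which includes level and trend, is named as the primary method.

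**The concern.** NAP compares ranks. When every control probe has the lowest possible score, any active probe above that score beats all of them, and by how much does not matter. The plan's own design makes this the expected situation for expressive labeling in all eight effectiveness questions.

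The plan defines effectiveness by the size of the increase relative to control. Yet for these questions NAP is the only number planned, and it comes with size bands. Sessions to mastery and sessions to fall below mastery are named only for the efficiency questions (RQs 5, 6, 11 and 12). A reader who sees *large* will take it to mean that much was learned or retained. It could equally describe a child who held one word of four throughout, while a child who reached mastery after a slow start could be labelled *weak*.

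**Working it through.** The plan gives no worked NAP value to reproduce, so the check applies its definition to possible probe series.

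**Inputs.**
- Control at 0% at every probe. This is inferred from the expectation of no increase and the pretest; the plan does not state it as a figure.
- Scale of 0, 25, 50, 75 and 100%. This assumes one labeling trial per word per probe, which the plan does not specify.
- The first comparison-phase probe is untaught, because each session runs the probe before teaching (section 5.0, Comparison Phase).
- About four weekly maintenance probes (section 5.0, Maintenance Phase).
- Two tie rules, since none is stated: a tie counts as overlap and scores 0, or a tie scores one half.

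**Formula.** Let f be the share of active probes above 0%. Against an all-zero control, an active probe above 0% wins every pair and an active probe at 0% ties every pair. Hence
- ties score 0: NAP = f
- ties score half: NAP = f + .5(1 − f) = .5 + .5f

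Enumerating every series of one to five probes on this scale confirmed both identities. The number of words correct does not appear in either.

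**Results, control at 0% throughout.**

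| Active series | f | NAP, tie = 0 | NAP, tie = ½ | Label |
|---|---|---|---|---|
| Maintenance: 25% at all 4 probes | 4/4 | 1.00 | 1.00 | large / large |
| Maintenance: 100% at all 4 probes | 4/4 | 1.00 | 1.00 | large / large |
| Acquisition: 0%, then 25% at 15 probes | 15/16 | .9375 | .969 | large / large |
| Acquisition: seven at 0%, then three at 100% (mastery met) | 3/10 | .30 | .65 | weak / weak |
| Acquisition: 0%, then three at 100% (fastest possible mastery) | 3/4 | .75 | .875 | medium / medium |
| Acquisition: 0, 0, 0, 25, 75, 75, 100% (mastery met) | 4/7 | .571 | .786 | weak / medium |

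The first four rows keep their labels under either tie rule. The .65 lies on the edge of its band; with eight zero probes it becomes .5 + .5 × 3/11 = .636. In the last row the unstated tie rule decides the label.

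**When a mastered set is labelled weak.** The band requires NAP ≤ .65. With ties at 0, f ≤ .65, so at least 35% of probes are at 0%. With ties at half, f ≤ .30, so at least 70% are at 0%.

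**If the control is not quite at floor.** Take ten control probes, one of them at 25%, with ties at half.
- Active 0% then nine at 25%: (9 × .5 + 81 + 9 × .5)/100 = .90, *medium*. With the control all zero it was .95, *large*.
- Active seven at 0% then three at 100%: (63 × .5 + 30)/100 = .615, still *weak*.

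**Receptive identification.** If guessing is independent with a chance of 1/6 to 1/4 per item, at least one of four is correct with probability 1 − (5/6)⁴ = .52 to 1 − (3/4)⁴ = .68. The zero-control premise fails for that outcome.

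**The case against.** The best defense is that NAP is not asked to measure amount. Visual analysis is primary and looks at level, where a flat 25% path and a 100% path plainly differ. The plan says NAP guides confidence about overlap, only one of five features, and reports the bands as tentative. It never says that a label decides a research question. All of this stands. A reader might infer that the effectiveness conclusions themselves would be wrong; the documents do not support that.

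The defense does not remove the point. For RQ1 the plan says separation of the data paths is shown by visual and statistical analyses together, so NAP does inform the judgement. It is also called an effect size, and no other number is planned for how much was learned in these questions.

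Three other stronger readings should be resisted.
- A reader might take the 0% control as fact. The plan expects no increase but allows a smaller one, and one control word in ten probes is enough to move a one-word series down a band.
- A reader might extend the point to every outcome. It does not reach receptive choice from a field of six.
- A reader might expect *large* against *weak* in any short series. Compare 0% then eleven probes at 25% (11/12 = .917, or .958 with ties at half) with three at 0% then three at 100% (3/6 = .50, or .75). The one-word child still scores higher, but the labels are *medium* against *weak* under one rule and *large* against *medium* under the other. The full reversal needs longer series, such as those in the table.

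**Conclusion.** The point holds for expressive labeling in RQs 1-4 and 7-10, on condition that the untaught words stay at floor, as the plan expects. NAP is then exactly f, or .5 + .5f, and carries no information on the number of words learned or retained. Under both tie rules, retaining one word and retaining four both score 1.00. A long one-word series can be *large* (.9375 or .969) while a series that ends in mastery is *weak* (.30 or .65).

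The identity is certain given an all-zero control. How often labels would actually reverse is unknown, because it depends on the children's learning paths and on how close to zero the control stays. The consequence is a misleading effect-size label on a supplementary statistic, not a wrong primary decision. It is worth correcting because the repair needs no new data.

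**What to change.** For expressive labeling in RQs 1-4 and 7-10:

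1. Report, per child, mean percent accuracy in the active set minus mean percent accuracy in the control set at the same probes. For acquisition, use all comparison-phase probes after the first teaching session while that set was being taught. For retention, use the maintenance probes. Add the across-child mean and range, and describe effect size from this difference.
2. Do not restrict acquisition to the last three taught probes. In a mastered set those are the criterion probes, so the stopping rule fixes them at 75% or more.
3. Keep NAP as an overlap statistic and state its tie rule. Scoring ties as half fits the plan's remark that Tau is a linear re-scaling: taking Tau as (higher − lower pairs)/all pairs, Tau = 2 × NAP − 1 holds in general only under that rule.
4. Attach no large/medium/weak labels when the control is at floor.

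On the series above with control at 0%, the maintenance differences become 25 and 100 points instead of 1.00 and 1.00. In acquisition, one word at 15 probes gives 25 points, late mastery gives (6 × 0 + 3 × 100)/9 = 33.3, and fastest mastery gives 100. The acquisition mean mixes speed with level, so it should be read beside the graph.

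The cost is a change of SAP wording and one more summary table from existing probe scores. Some effects that NAP would call *large* will be shown as one-word gains.
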